Methods: This is a single arm study to assess the effectiveness of an experimental telehealth intervention within the treatment of ESLD, and compare it with a historic cohort. All inpatients with advanced liver disease and at least 1 complication will be eligible to participate. The study group receives the Telehealth intervention and will be given an ipad/smartphone preloaded with the instruments used for symptom monitoring and cognitive function assessment during the hospital admission. A research coordinator will consent the patients and conduct a 30-minute introduction to use of device on the day of enrollment (within 24-48 hours of admission). The second assessment will be done on day 2, and third assessment on day of discharge. After that, the patient will be told to do the study assessments daily at home. The study assessment results will be reviewed by the providers on the same day, and based on the severity scores clinical actions will be taken and documented.

IV. Expected Research Outcomes and Benefits -
--

Primary Outcomes:

- 1) Healthcare utilization (30 and 90-day readmission)
- 2) Changes in severity scores of symptoms and quality of life over time.

3) Patient experience/satisfaction.

Benefits of the research: Applying telehealth intervention (inclusive of remote monitoring of symptoms and cognitive function) with a well-defined clinical algorithm at the time of discharge of patients with ESLD, who are prone to impaired quality of life, adds a **new dimension** to the care delivery model. This new post-hospital discharge algorithm is expected to have positive effects on many parameters, including readmission rates, patient satisfaction, and above all on the health outcomes. Arguably, these improvements will reduce health care costs among a group of patients with ESLD, who are high utilizers of healthcare services. Benefits to individual patients include monitoring of their own symptoms, and cognitive function, which will allow early detection of hepatic encephalopathy and/or other complications.

VII. Evaluation Component and Research Evaluative Procedures - Oversight and Statistical Tests

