“HGE healthcare solutions” is a group of experts who have pioneered some work in telehealth, and created a smartphone based COPD app (Chronic Obstructive Pulmonary Disease), which assesses daily symptoms and triggers alerts to providers for immediate treatments. This app has shown to improve health outcomes and reduce hospitalizations by changing the approach of health care to proactive than reactive. ^{v vi} We will be partnering with this company in creating and delivering our telehealth intervention. The company operates on a HIPAA secured platform, which maintains confidentiality and security of the data. They also offer technical assistance to end users during normal business hours.

(3) Research Design, Methods and Activities -
--

Methods: This is a single arm trial to assess the effectiveness of an experimental telehealth intervention within the treatment of ESLD, and compare it with a historic control. The study patients continue to receive the routine standard of care, which may involve addressing symptoms based on individual needs and circumstances. All participants will be given an ipad/smartphone preloaded with the instruments used for symptom monitoring and cognitive function assessment. A research coordinator will consent the patients and conduct a 30-minute introduction to use of device on the day of enrollment. Repeat assessments will be done as shown in **Table 1** above. All patients will receive the standard of care discharge planning, including discharge instructions and a confirmed follow-up ambulatory visit within 2-4 weeks.

Inclusion Criteria: All patients being discharged from the inpatient liver practice of the Einstein Healthcare Network (EHN) who meet the following criteria will be eligible.

- ✓ Patients must be age 18 years or older
- ✓ Ability to provide informed consent, and must be able to cognitively answer questionnaires
- ✓ Patients who received a diagnosis of Advanced Liver Disease with at least 1 of the complications (Hepatorenal Syndrome, Portal Hypertension, Ascites, Hepatic Encephalopathy)
- ✓ Patient must be able to read/ speak English
- ✓ Patient must have a support person

Exclusion Criteria:

- ✓ Cognitive impairment which precludes participation
- ✓ Projected survival, in the opinion of the provider, of less than six months
- ✓ Current psychosis or confusion, precluding a patient from being consented
- ✓ Patients being discharged to nursing homes

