- ✓ Patients with red green color blindness (as they will not be able to respond to stroop test questions).

Telehealth Intervention:

Patients will receive a 30-minute introduction to the use of ipad/smartphone, and instructions to respond to the following assessments. Initial assessments will be performed on the day of enrollment, and all of them will be repeated periodically (**Table 1**), for a total of 3 months study

participation. The assessments include the following: Pain (severity, location), shortness of breath (at rest or with mild activity), cognitive function assessment (drowsy, hard time concentrating, irritable, trouble remembering things, slurred speech, unsteady gait), and stroop test (color matching test, one cycle lasts 45 seconds).

Weight monitoring: Monitoring weight will allow assessment of fluid retention in ESLD patients, and help detect any development/ worsening of ascites. Patients will be instructed to enter their daily weights for the first month, and then every week for next 2 months. Any weight gain of more than 2 lbs within 1-2 days for 3 consecutive days will trigger a phone call by the providers.

A simplified step by step guide summarizing the instructions will be included with the device. Patients will be given a toll-free number that will be available during work hours (9am to 5pm) for any technical issues, and will be urged to complete assessments by 11 am on a daily basis.

Site: Levy 7 is the home of the “Liver Care Center at Einstein”, a 15 bed inpatient unit dedicated to the care of patients with liver disease. This inpatient unit is the site of identification and recruitment of patients in this project.

Recruitment methods: The research coordinator will contact eligible patients within 24-48 hours of admission and conduct informed consent. All patients who consent will be then randomized to either of the 2 groups. We assume 3-4 patients will be enrolled per week, for 7 months of enrollment period.

Sample size and power: Assuming a baseline risk of readmission in the historic control of 40% and 10% attrition rates, a sample size of 50 patients will be sufficient to detect a difference of 35% or greater in the intervention group. Accepting a type I error rate of no more than .05, and a Type II error rate of .20, we will have 80% statistical power to detect a difference of this magnitude or larger.

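### The study group is filtered on factors that can affect readmission, and the plan neither says that the historic control meets the same criteria nor adjusts the comparison for severity

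*Combined protocol and SAP*

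**What the plan says.** **Design.** Section II (Methods) describes a single-arm study that will "compare it with a historic cohort". Section XI(3) (Methods) repeats this: "and compare it with a historic control". Readmission at 30 and 90 days is the first primary outcome (Section IV) and specific aim 2 (Section XI(1)).

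**Study group.** Section XI(3) requires age 18 or over, advanced liver disease with at least one listed complication, English, and the ability to consent and answer questionnaires. It adds "Patient must have a support person". The exclusions are cognitive impairment that prevents participation, "Current psychosis or confusion, precluding a patient from being consented", projected survival under six months, discharge to a nursing home, and red-green colour blindness. Hepatic encephalopathy is one of the four qualifying complications.

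**Comparator.** The only figure is in Sample size and power: "Assuming a baseline risk of readmission in the historic control of 40% and 10% attrition rates". The source, calendar period, size, eligibility rules and index admission are not given. Nor is it stated whether 40% is a 30-day or a 90-day rate.

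**Analysis.** Section VII (Statistical Tests) describes readmission within the study group and uses MELD to test whether the effect varies with severity. The Analysis plan in Section XI(3) has severity, diagnosis, disease duration and comorbidities taken from records, and mentions linear correlation and regression without naming an outcome or covariates. The only limitation listed is attrition.

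**A conflicting sentence.** Recruitment methods says: "All patients who consent will be then randomized to either of the 2 groups".

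**The concern.** With no concurrent control, the readmission claim depends on the historic patients being like the enrolled ones. Several study filters plausibly bear on readmission without any device: a support person at home, being clear-headed enough to consent, an expected survival of at least six months, and not going to a nursing home.

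The point is specific to this disease. Encephalopathy qualifies a patient for the study, and its early detection is a stated benefit, yet confusion severe enough to prevent consent keeps a patient out. Nothing in the plan removes such patients from the historic cohort.

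If the cohort is taken without matching criteria and compared crudely, any difference due to selection is credited to telehealth. Testing MELD as an effect modifier does not correct for a difference in MELD between the cohorts.

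**Working it through.** **1. The plan's own figure.** Inputs from Sample size and power: control rate 40%, difference 35%, alpha .05, power 80%, attrition 10%, N = 50. Sidedness, and whether 35% is absolute or relative, are not stated; two-sided is assumed here.

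- Two groups, absolute difference (40% v 5%, mean 22.5%): n per group = [1.960·√(2·0.225·0.775) + 0.842·√(0.40·0.60 + 0.05·0.95)]² / 0.35² = 21.1, so 22. Then 22/0.9 = 24.4, so 25 per group and 50 in total. This reproduces N = 50.
- One group against a fixed 40%, absolute difference: n = [1.960·√(0.40·0.60) + 0.842·√(0.05·0.95)]² / 0.35² = 10.7, so 11, or 13 after attrition.
- One group against a fixed 40%, relative difference (0.40 × 0.65 = 26%): n = 90.2, so 91, or 102 after attrition.

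Of these readings, the one that gives 50 has two groups of 25, which fits the randomisation sentence better than a single arm of 50.

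**2. Which criteria are stated for which group**

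| Criterion | Study group | Historic control |
|---|---|---|
| Advanced disease with a complication | required | not stated |
| Support person | required | not stated |
| English | required | not stated |
| Able to consent and answer questionnaires | required | not stated |
| Consent-precluding confusion | excluded | not stated |
| Projected survival under six months | excluded | not stated |
| Nursing-home discharge | excluded | not stated |
| Severity adjustment of the comparison | none planned | none planned |

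**3. How far selection could move the rate.** The documents give no figures for this, so these are assumptions: 40% is an unfiltered rate, a fraction f of historic patients would have met the criteria, and those who would not are readmitted RR times as often. The rate in comparable patients is then 0.40 / [f + (1 − f)·RR].

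| f | RR | Rate in comparable patients |
|---|---|---|
| 0.75 | 1.25 | 0.40/1.0625 = 37.6% |
| 0.75 | 2 | 0.40/1.25 = 32.0% |
| 0.50 | 1.25 | 0.40/1.125 = 35.6% |
| 0.50 | 2 | 0.40/1.5 = 26.7% |

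**4. Effect on a test with no device effect.** Evaluable patients: 50 × 0.9 = 45. Assume an exact binomial test against a fixed 40%, two-sided .05. At 40%, P(X ≤ 11) = 2.2% and P(X ≤ 12) = 4.5%, so a reduction is significant at 11 or fewer readmissions.

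| True rate, no device effect | P(X ≤ 11) |
|---|---|
| 40% (nominal) | 2.2% |
| 38% | 4.0% |
| 36% | 6.9% |
| 32% | 17.8% |
| 30% | 26.2% |
| 26.7% | 44.3% |

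With 45 historic patients in place of a fixed rate (two-sample, two-sided), the chance at a true 30% is 16.6% rather than 26.2%.

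**5. Could selection produce the full 35 points?** With f = 0.5, comparable patients would need a 5% rate. The others would then be at (0.40 − 0.5·0.05)/0.5 = 75%, a ratio of 75/5 = 15. That is not plausible.

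**The case against.** The strongest reply is that the documents do not define the control, which is different from saying that it is unrestricted. A reader might infer that the 40% comes from an unfiltered cohort. The text does not support that; the 40% may already come from similar patients. What stands is that the plan does not say so.

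A reader might also infer that the bias must favour the device. Direction is likely but not certain. The study group must have advanced disease with a complication, so a historic cohort with milder disease would push the other way.

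It is also tempting to treat consent at 24-48 hours as a hard screen that removes everyone admitted with encephalopathy. Section II and Recruitment methods give that timing. However, Section XI(4)(c) approaches patients discharged from the unit and allows one or two days to decide, and only confusion that prevents consent is excluded. A patient whose confusion clears may enrol.

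Nor do the documents settle that readmission is the only outcome compared externally. Statistical Tests refers to differences between two groups for the defined outcomes in general.

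The randomisation sentence matters most. Concurrent randomised groups would remove this problem, and N = 50 reproduces as two groups of 25. But both Methods sections and the sample size text name a historic comparator, so the sentence calls for reconciliation and does not answer the point.

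Finally, no readmission test against the control is written down, and the unspecified regression could be used for adjustment. That is so, but nothing commits the analysis to it.

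**Conclusion.** The point holds in this form: the study group is explicitly filtered, the plan does not state that the historic control meets the same criteria, and no severity adjustment of the readmission comparison is planned. A difference, probably but not certainly in favour of the device, could therefore arise from selection alone.

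The size is illustrative. Across true rates of 38% down to 26.7% in comparable patients, a device with no effect would show a significant reduction with probability about 4% to 44%, against about 2% nominally. This rests on assumed eligible fractions and risk ratios, 45 evaluable patients and a fixed-rate exact test, none of which the plan specifies apart from the 50 patients and 10% attrition behind the 45. The claim is limited to a misleading significant result; selection is unlikely to explain an absolute 35-point difference.

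It should be corrected before outcomes are examined, because a primary outcome depends on it.

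**What to change.** 1. Reconcile the randomisation sentence in Recruitment methods with the single-arm design in both Methods sections. If there are concurrent randomised groups, this point falls away.
2. If the historic comparator stays, define it in both Methods sections: patients discharged from the same inpatient unit over stated dates, one index admission each, with the same 30- and 90-day windows.
3. Apply every criterion that can be read from the chart, including discharge destination. Exclude only confusion of a degree that would have prevented consent. Keep other patients with hepatic encephalopathy, since it is a qualifying complication and removing them all could make the control healthier than the study group.
4. Abstract MELD, encephalopathy at admission, comorbidities and prior admissions for both cohorts. Make the main readmission comparison adjusted for, or weighted on, MELD and encephalopathy at admission, with the crude comparison secondary.
5. Re-estimate the 40% in the filtered cohort and restate the detectable difference for N = 50.
6. List residual selection (support person, consent, projected survival) under Limitations.

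The cost is protocol wording and additional chart abstraction. Some criteria, notably the support person, are charted imperfectly. The filtered baseline risk may fall below 40%, which would change what 50 patients can detect.

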I. Research Project Title, Purpose, Anticipated Project Duration and Inclusion of Proprietary Information

Protocol Version: May 8 2017

Investigators: [name], [name], [name]

Title:

Remote monitoring of symptoms and cognitive function using Telehealth: *T- Liver* project

Purpose:

End-Stage Liver Disease (**ESLD**) is one of the ten leading causes of death in US. It is marked by episodic acute exacerbations of the underlying liver disease which often leads to severe symptoms, poor quality of life, mental deterioration and repeated hospitalizations. The **overall purpose** of this project is to introduce a telehealth based intervention (involving remote monitoring of symptoms and cognitive function assessment) initiated during the time of hospital admission of ESLD patients. This will support enhanced clinical care and improve self-management in ESLD population. In addition, it will reduce healthcare utilization, improve medication adherence and overall health outcomes.

II. Research Project Overview

The **primary goal** is to develop and implement a systematic clinical approach for remote monitoring of symptoms and cognitive function in ESLD patients, through developing a telehealth based intervention. The intervention includes assembling specific apps on an ipad/smartphone/tablet through a web based secured system, having patients respond to periodic assessments and transmission of results instantly to providers, who will follow specified clinical pathways stratified by severity scores.

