Retention strategies: Patients will be informed about the purpose of the study and their responsibilities at the time of consent by the research coordinator. All patients with a support person will be eligible. Strategies (i.e. education about value of study participation) will be added if recruitment rates fall within 20% of target.

Analysis plan: Medical records will be utilized to capture the disease severity, diagnosis, duration of liver disease and presence of comorbidities. Patients enrolled into the study will be followed up for 6 months. Descriptive and analytics statistics will be done using linear correlation and regression. We will compare the clinical markers at baseline with 3 month value using unpaired t test.. .

Limitations:

Patient Attrition: this is an anticipated problem, as physical and cognitive deterioration may make the completion of questionnaires difficult. This limitation will be minimized by the short interval assessments and completion of study at 3 months.

(4) Protection of Human Subjects -

- (a) **Risks to subjects:** There is no medical risk to any participant and no sharing of protected health information in this project. It is completely up to the participants to agree for this study. Refusal for participation will not impact their health care in the office. There are minimal risks to participants related to their completion of survey questionnaires. There may be some emotional distress as they complete the symptom and quality of life questions, but this will influence and enhance their own care. Patients may have technical difficulties, which will be addressed through availability of a help desk and the research coordinator during work hours.
- (b) **Adequacy of protection against risks:** There are no known risks in this study. All study personnel have completed the IRB required CITI training, and will be trained appropriately. Confidentiality is maintained through Einstein's secured system and the secure administration through HGE. The PI and Co-Investigator will be available to answer any of the patient's concerns. The research coordinator will conduct an in-depth informed consent explaining the purpose of the project, and the expectations from patients to respond to the assessments in a timely way. All the information collected is through a secured password protected system, which allows encrypted data transmission to the providers

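### Weight is entered weekly in months 2-3, but the only stated weight alert needs weights 1-2 days apart, so it cannot operate for essentially all of those two months

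*Combined protocol and SAP*

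**What the plan says.** Three consecutive statements in the weight monitoring paragraph (section XI(3), Telehealth Intervention) define this part of the intervention.

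- Purpose: "Monitoring weight will allow assessment of fluid retention in ESLD patients", and so help to pick up new or worsening ascites.
- Schedule: "Patients will be instructed to enter their daily weights for the first month, and then every week for next 2 months".
- Alert: "Any weight gain of more than 2 lbs within 1-2 days for 3 consecutive days will trigger a phone call by the providers".

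No other weight threshold appears in the text available for this review. Four other statements bear on the point.

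- The Methods text in section II says of the period after discharge: "After that, the patient will be told to do the study assessments daily at home". It adds that providers review the assessment results the same day and act on severity scores.
- The Research Project Overview says that results go to providers "who will follow specified clinical pathways stratified by severity scores". The pathways themselves are not reproduced.
- Section XI(3) refers to Table 1 for the repeat-assessment schedule. The table is not in the available text.
- Standard discharge planning includes "a confirmed follow-up ambulatory visit within 2-4 weeks".

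**The concern.** The alert compares weights taken one or two days apart. The schedule supplies such weights only in the first month. After that, a patient who enters every weight exactly as instructed still cannot set off the alert. Weight is the measure the protocol chooses for detecting fluid build-up, and ascites is one of the complications that qualify a patient for the study.

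Two things are at stake. The first is patient safety. For two of the three months, a rapid gain leads to no prescribed call, and a provider who does see a weekly weight has no stated threshold for acting on it. The second is interpretation. Section VII plans to summarise process data as a measure of intervention fidelity. An absence of weight-triggered calls after the first month could be read as stable patients, when the rule could not have fired.

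**Working it through.** The plan states no count of days on which the alert can operate, so there is no figure to reproduce. The count below comes from listing the entry days.

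**Inputs from the weight paragraph.** Daily entry for the first month, then weekly for two months. The alert needs a gain above 2 lb within 1-2 days, for 3 consecutive days.

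**Assumptions.** The protocol gives no day counts. I take a first month of m = 30 days and T = 90 days in total, with perfect entry, and then vary these.

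**Two readings of the rule.**
- Loose: day t can be evaluated if it has a weight and there is another weight on day t-1 or t-2. This ignores the 3-day condition.
- Strict: the loose condition holds on each of days t-2, t-1 and t.

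**Month 1.** Under the strict reading the first evaluable day is day 4, because days 2, 3 and 4 each have an earlier weight within 2 days. Days 4 to 30 qualify: 30 - 3 = 27 days, and 27/90 = 30% of participation.

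**Months 2-3.** Successive weekly entries are 7 days apart, and 7 > 2, so no two of them can be paired. The only possible pairing is between the first weekly entry and the last daily weights.

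| First weekly entry | Evaluable days after day 30, loose | Strict | Days with no working alert (loose) |
|---|---|---|---|
| Day 31 | 1 (day 31) | 1 (day 31) | 59 of 60 |
| Day 32 | 1 (day 32, against day 30) | 0 | 59 of 60 |
| Day 33 to 37 | 0 (at least 3 days after day 30) | 0 | 60 of 60 |

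The 1-2 day window alone produces this result. The 3-day condition only reinforces it.

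**Sensitivity (loose reading).** With T = 90 and m from 28 to 31 days, the days with no working alert range from 58 to 62. With T up to 92 the range is 58 to 64, and with an 84-day study it is 52 to 56.

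**Illustration (assumed steady gain of 1.1 lb/day).** Over two days the gain is 2 x 1.1 = 2.2 lb, just above the limit. If the gain starts after day 10, the 2-day gain exceeds 2 lb on days 12, 13 and 14, so the call comes on day 14, after 4 x 1.1 = 4.4 lb. In the weekly phase the same rate gives 7 x 1.1 = 7.7 lb between two entries and no call. This shows how the rule behaves and does not forecast how patients will gain weight.

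**The case against.** **Part of the plan is unseen.** Table 1 and the clinical pathways could hold a weekly weight rule, and their absence from the available text is not a defect of the plan. This stands as a limit. Against it, Table 1 is cited for the assessments while weight has its own paragraph and schedule, and the pathways are described as stratified by severity scores, with no weight score mentioned.

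**Assessments are daily and reviewed the same day.** If these statements cover weight, a provider would see it promptly. However, the list of assessments in the Telehealth Intervention section names pain, shortness of breath, cognitive function and the Stroop test, not weight. The specific weight schedule governs weight. Same-day review may still bring a weekly weight to a provider's notice, but no threshold for action is stated.

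**The sentences do not contradict each other.** A daily alert phase followed by lighter weekly tracking is a coherent step-down, and the protocol does not say that the alert is the only ground for a call. That is fair. The defect is that no action rule is stated for weekly weights, while the one stated rule cannot work on them.

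**Weekly may mean daily weights uploaded once a week.** This is possible but less natural. The rule would then be checked up to a week late.

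**Stronger readings a reader might infer.**
- That patients go unmonitored after month 1. The documents do not support this: symptom, cognitive and Stroop assessments run for the 3 months of participation, standard care continues, and safety is reviewed monthly. The confirmed clinic visit falls at about the time daily weights end, so it covers little of months 2-3.
- That the gap will raise 90-day readmission. Nothing in the documents allows such an effect to be sized.
- That the alert covers a stated share of the 90-day readmission window. Enrolment is in hospital, readmission is possible only after discharge, and the protocol does not say when the first month of weights begins. The counts above are therefore days of weight entry, not days at risk of readmission.

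**Conclusion.** The concern holds as a gap in the weight alert. On the natural reading of the schedule, the only stated rule is inoperative for essentially all of months 2-3: 59 or 60 of 60 days with a 30-day first month and 90 days of participation. The exact figure depends on the first weekly entry. The conclusion rests on weekly meaning one weight per week, and on neither Table 1 nor the pathways holding a separate weekly rule.

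The point is operational. Weight is not among the primary outcomes and is not named in any planned analysis, so no estimate or test in the plan is invalidated. It is still worth correcting, because a safety rule followed exactly cannot function for about two of the three months it is meant to serve, and the remedy is small.

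**What to change.** Keep the weekly schedule and add one sentence to the weight paragraph: in months 2-3, a gain since the last weekly entry above a stated number of pounds leads to a provider call and a return to daily weights. The investigators should fix the value before enrolment. If Table 1 or the pathways already contain such a rule, a cross-reference is enough. Report weight-triggered calls separately for the daily and weekly phases.

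An assumed threshold range of 2 to 5 lb shows the trade-off. Take the 1.1 lb/day gain, entries on days 37, 44 and 51, and a last stable day anywhere from 37 to 43.
- 2 lb: the call comes 7, 6, 5, 4, 3, 2 or 8 days after the last stable day (mean 35/7 = 5).
- 5 lb: the call comes 7, 6, 5, 11, 10, 9 or 8 days after it (mean 56/7 = 8).

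These delays describe the proposed remedy under assumed values, not the protocol.

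The cost is one sentence, one app setting and some extra calls for ordinary weight variation, with more such calls at a lower threshold. Daily weights for all three months would also close the gap. With a 30-day first month that adds 60 - 9 = 51 or 60 - 8 = 52 entries per patient, in a population where the Limitations section already expects that "physical and cognitive deterioration may make the completion of questionnaires difficult". The weekly trigger is the lighter choice.

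### The recruitment text randomizes patients to two groups in a study described as single-arm, and the stated 80% power is not the power of a single-arm study of 50

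*Combined protocol and SAP*

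**What the plan says.** Section II (Methods) gives the design: "This is a single arm study to assess the effectiveness of an experimental telehealth intervention within the treatment of ESLD". The comparator is named in the same sentence: "and compare it with a historic cohort". Section XI(3) (Methods) repeats the design, "This is a single arm trial to assess the effectiveness of an experimental telehealth intervention within the treatment of ESLD", there with a historic control, and adds: "All participants will be given an ipad/smartphone preloaded with the instruments used for symptom monitoring and cognitive function assessment".

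Section XI(3) (Recruitment methods), on what follows consent: "All patients who consent will be then randomized to either of the 2 groups".

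Section XI(3) (Sample size and power) comes directly after. Its starting point is: "Assuming a baseline risk of readmission in the historic control of 40% and 10% attrition rates". Its claim about the number of patients is: "a sample size of 50 patients will be sufficient to detect a difference of 35% or greater in the intervention group". With type I error of .05 and type II error of .20, it concludes: "we will have 80% statistical power to detect a difference of this magnitude or larger". It does not state the test, whether it is one- or two-sided, whether 35% is absolute or relative, whether the 40% is a 30-day or 90-day rate, or how many historic patients it rests on.

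**The concern.** A historic control cannot be randomized, and a study that gives the device to every participant has no second group to randomize to. The sentence is an instruction for what happens after consent. If it were followed with 50 patients, about 25 would receive the intervention and 22 or 23 of them would be evaluable, instead of 45.

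The power paragraph is the only justification of the sample size. If its figures do not belong to the single-arm design, a reader cannot tell what fall in readmissions the study can detect.

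**Working it through.** **1. The design passages side by side**

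- Single arm: section II (Methods) and section XI(3) (Methods), with the device for all. Section VIII says that providing the device removes the access disparity for those who take part. Section XI(4)(c) goes straight from agreement to take part to explaining the device.
- Two randomized groups: the one sentence under Recruitment methods. The protocol gives no allocation ratio, randomization method or control-group procedure.

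**2. Inputs**

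From Sample size and power: 40% baseline, 35% difference, 50 patients, 10% attrition (50 × 0.9 = 45 evaluable), alpha .05, power 80%. Assumed: two-sided test, a fall in readmissions, 1:1 allocation where there are two groups. The two readings of 35% are absolute (40% to 5%) and relative (40% × 0.65 = 26%).

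**3. Reproducing the stated 50**

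Two 1:1 groups, pooled test without continuity correction, 40% v 5%, mean rate 0.225:

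n per group = [1.960 × √(2 × 0.225 × 0.775) + 0.842 × √(0.40 × 0.60 + 0.05 × 0.95)]² / 0.35² = (1.157 + 0.451)² / 0.1225 = 21.1, so 22.

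After attrition: 22 / 0.9 = 24.4, so 25 per group and 50 in all (49 if the total of 44 is inflated instead). Power at 22 per group is 82% (77% by Fisher's exact test). Other standard formulas give 34 to 60 enrolled, so the match depends on the formula chosen.

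**4. The same target in a single arm against a fixed 40%**

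n = [1.960 × √(0.40 × 0.60) + 0.842 × √(p(1 − p))]² / (0.40 − p)²

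- p = 0.05: 10.7, so 11 (12 by exact binomial), or 13 to 14 enrolled.
- p = 0.26: 90.2, so 91 (98 by exact binomial), or 102 to 109 enrolled.

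Neither reading gives 50.

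**5. Power of a single arm with 45 evaluable**

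Against a fixed 40%, the exact binomial test rejects at 11 or fewer readmissions (lower tail .0216). Against a historic sample, a pooled two-sample test was used.

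| Comparator | Power, 40% to 5% | Power, 40% to 26% | Rate at which power is 80% |
|---|---|---|---|
| Fixed 40% | over 99.9% | 48% | about 20.5% |
| Historic sample of 45 | 98.7% | 29% | about 14% |
| Historic sample of 100 | over 99.9% | 36% | about 17% |
| Historic sample of 200 | over 99.9% | 41% | about 19% |
| Historic sample of 500 | over 99.9% | 45% | about 20% |

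The detectable fall against a fixed 40% is therefore about 19 points.

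**6. Sensitivity to attrition**

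The Limitations text describes attrition as difficulty completing questionnaires, so readmission data may be complete. With 50 evaluable against a fixed 40%, the exact test rejects at 12 or fewer. Power for 5% stays over 99.9%, power for 26% is 45% (53% by z test), and 80% power is reached at about 20.3% (21.5% by z test). The conclusion does not change.

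**The case against.** The strongest reply is that this is one stray sentence. The protocol gives staff no means of randomizing anyone, and sections VIII and XI(4)(c) assume that every participant has the device. That stands: the intended design can be read with fair confidence, and a trial run with half its patients untreated is a remote prospect. But the sentence is a current instruction in the recruitment section and nothing elsewhere corrects it.

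A second reply is that the power paragraph does refer to the historic control and to one intervention group, and that on the absolute reading 50 is indeed sufficient, so the error is on the safe side. Sufficiency on that reading is accepted. The paragraph still gives 80% as the power, which is wrong on both readings, and it leaves out the effect that the study can detect.

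Three stronger readings are tempting, and the documents do not support them.

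- A reader might infer that the trial is too small. That follows only if 35% is relative, and no scale is stated.
- A reader might infer that the 50 was carried over from a randomized design. The arithmetic fits, but other formulas give other totals and the paragraph names a historic control, so this remains an inference.
- A reader might count the references to two groups and to study arm under Statistical Tests in section VII as further contradictions. They can mean the study group and the historic cohort, so they need defining and no more.

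**Conclusion.** Wrong as written. The randomization sentence and the single-arm description with the device for all cannot both stand, whatever the arithmetic.

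The power error is a consequence. If single arm stands, 80% understates the power on the absolute reading (at least 98.7% in every case examined) and overstates it on the relative reading (29% to 48% with 45 evaluable). These figures rest on a two-sided .05 test, 10% attrition applied to readmission data, and either a fixed 40% or a historic sample of 45 to 500. The documents settle neither the scale nor the comparator, so both are questions for the sponsor. If two randomized groups were meant, the stated size is adequate for 40% v 5% under the pooled test.

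**What to change.** Reconcile Recruitment methods with the Methods text in sections II and XI(3).

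**If single arm stands:**

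- Delete the randomization sentence.
- State whether 35% is absolute or relative, whether 40% is a fixed rate or comes from a historic sample (and its size), and whether it refers to 30 or 90 days.
- Restate the power or the detectable difference from the matching row of the table above.
- Name one readmission test in both Statistical Tests (section VII) and Analysis plan (section XI(3)). Examples are an exact binomial test against a fixed rate, or a two-sample comparison of proportions with the cohort. Neither is in the plan now: those sections describe change within the study group, paired and unpaired t tests, and regression.
- Define the two groups and study arm in section VII.

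**If two randomized groups were meant:** 50 can stand for 40% v 5%, and the Methods text in sections II and XI(3) must be rewritten, with the allocation method and the control-group procedure added.

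**Minor:** 3 to 4 patients per week over 7 months (30.4 weeks) is about 91 to 122 patients and should be aligned with 50.

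**Cost:** for a single arm, wording of the design, power and analysis text, with no extra patients requested. If the relative reading was meant, the stated power becomes less favourable.
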